CHOD-PAP: Cholesterol oxidase phenol-aminophenazone CI95%: Confidence interval 95% CKD-EPI: Chronic Kidney Disease Epidemiology Collaboration DEC: Dermal Electrochemical Conductance DECODING: Dermal Electrochemical Conductance in Diabetic Neuropathy DM: Diabetes mellitus DSPN: distal symmetric polyneuropathy EMG: electromiography HLD: High density lipoprotein HPLC: High Resolution Liquid Chromatography ICS: Institut Català de la Salut -Catalan Institute of Health IDIAP : Institut d'Investigació en Atenció Primària – Primary Care **Research Institute**

IFG: Impaired fasting glucose IGT: Impaired glucose tolerance LDL: Low density lipoprotein MDRD: Modification of Diet in Renal Disease MFT: Monofilament testing MNI : Michigan Neuropathy Instrument NDS: Neuropathy Disability Score NSS : Neuropathy Symptoms Score OGTT: Oral glucose tolerance test PN: polyneuropathy QOL-DN: Quality of Life Questionnaire-Diabetic Neuropathy ROC: Operative Receptor Characteristics UENS: Utah Early Neuropathy Scale VO2 max: Maximum Oxygen Volume WHO: World Health Organization

ABSTRACT:

Diabetes mellitus is the leading cause of polyneuropathy in the Western world. Diabetic neuropathy is a frequent complication of diabetes and may have great clinical transcendence due to pain and possible ulceration of the lower extremities. It is also a relevant cause of morbidity and mortality in patients with diabetes. Although the cause of polyneuropathy in patients with diabetes is only partially known, it has been associated with chronic hyperglycaemia suggesting the possible aetiopathogenic implication of advanced glycosylation end-products. The strategy of choice in the medical management of diabetic neuropathy is early detection since glycaemic control and the use of certain drugs may prevent or slow the development of this disease. Diabetic neuropathy most often presents with a dysfunction of unmyelinated C-fibers, manifested as an alteration of the sweat reflex of the eccrine glands. This dysfunction can now be demonstrated using a newly developed technology which measures dermal electrochemical conductivity. This noninvasive test is easy and cost-effective. The aim of the present study is to evaluate the feasibility and effectiveness of dermal electrochemical conductance measurement (quantitative expression of the sudomotor reflex) as a screening test for the diagnosis of diabetic neuropathy in patients in primary care.

5

INTRODUCTION

The prevalence of diabetes mellitus (DM) is very high in Spain, being nearly 14% according to oral glucose tolerance test (OGTT) results (1). The management of DM requires a significant consumption of healthcare resources, mainly in relation to the care of vascular complications. Among the late microvascular events which may develop in patients with DM, polyneuropathy (PN) is the most common and disabling, and is the leading cause of morbidity and mortality in these patients (2). Indeed, in Spain, the leading cause of neuropathy is DM, with its prevalence increasing with the presence of DM and other risk factors such as obesity (3).

PN is defined as the presence of symptoms and/or signs of peripheral nerve dysfunction in people with DM after the exclusion of other possible causes (4). The Toronto Panel Consensus on PN defined this disorder as "symmetrical, depending on large fibers, sensory-motor attributable to metabolic and microvessel disorders, as a result of chronic hyperglycemia and other risk factors" (2). In patients with PN, thin fibers (autonomic system - sweating) and thermal and tactile sensitivity are first affected, followed by the involvement of large fibers, presenting an altered vibrating sensation which eventually alters electromyography (EMG) patterns. Therefore, dysfunction of sweat reflex in small distal fibers is one of the earliest changes to be detected in these patients (5).

The most common clinical presentation of PN is distal symmetric polyneuropathy (DSPN), being predominantly sensory in 80% of cases (3). Pain is the most important symptom, being described as burning or flashing, lancinanting, deep, and with frequent exacerbations during rest (4). Pain often affects the quality of life of these patients, and

it is a frequent cause of depression and/or anxiety (6). Moreover, some patients may develop hypoesthesia, which may lead to severe foot lesions (7).

The prevalence of DSPN varies greatly according to the population, definition and detection method. The Rochester study, including more than 64,000 patients, reported the prevalence of PN to be between 66% and 59% for type1 DM and type 2 DM, respectively (8). The 3rd report of the Technical Study Group of Diabetes of the World Health Organization (WHO) described a prevalence of 40% (8), and 50% in patients with more than 25 years of DM evolution. Pirart *et al.* (9) reported a prevalence ranging from 25 to 48% (7,10-17), while in Spain, Cabezas-Cerrato *et al.* published a figure of 24.1% (11). DSPN-related factors are: age, DM duration, metabolic control, male gender, acute myocardial infarction, hyperlipidaemia (especially hypertriglyceridaemia), smoking, and general cardiovascular risk factors (2,15,16,18). Puig *et al.* (15) also included urinary albumin excretion as a risk factor of presenting DSPN.

The diagnosis of DSPN is commonly made based on signs and symptoms and usually includes the use of several questionnaires such as the Neuropathy Disability Score (NDS), the Neuropathy Symptoms Score (NSS) and the Michigan Neuropathy Instrument (MNI). These questionnaires are easy to perform and are reproducible, sensitive and adequate for use in a screening program (16). Additionally, It was included a short scale (UENS - Utah Early Neuropathy Scale) to screen early neuropathy (17). This sensitive, fast and practical test, has 5 items and their score ranges from 0 to 42 points.

7

There are many confirmatory tests, including measurements of nerve conduction velocity (EMG) and biothesiometry or skin biopsy. However, those most commonly used are the measurement of altered sensations using a vibrating tuning fork with 128 Hz and/or pressure with Semmes-Weinstein 5:07 monofilament (18). Monofilament testing (MFT) is widely accepted and recommended by all scientific societies because of its validity, predictive risk, efficiency and simplicity. Feng *et al.* (19) reported that MFT has a sensitivity of 57-93%, a specificity of 75-100%, a positive predictive value of 36-94% and a negative predictive value of 84-100% compared to the measurement of nerve velocity by EMG. Although electrophysiological measures are more objective and reproducible, they are limited in that they only detect dysfunction based on the presence of thicker and faster (myelinated) fibers and show their involvement later. Consequently, EMG is a specific, albeit very insensitive, test.

Recently developed non invasive techniques are more reproducible and reliable for the detection of early dysfunction of small fibers. One of these new techniques involves the measurement of **dermal electrochemical conductance** (**DEC**) or sudomotor dysfunction index and has been evaluated by well-designed studies (Calvet, Dupin, Winiecki, Black, 2013; Casellini 2013; Devigili 2008; Peltier 2009) which support its use as a screening test (20).

Ramachandran *et al* (21) studied the use of DEC to detect diabetes and other disorders of glucose metabolism. In a study on the use of DEC Casellini *et al* (5) applied a PN test which showed a low sensitivity of 78% and a specificity of 92% in diabetic patients without neuropathy compared to other subjects with neuropathy and a control group. In this latter study, correlation with clinical parameters showed adequate reproducibility of the results, particularly in regard to the measurements of the feet (5). Several other studies (22) also obtained significantly lower DEC values on comparing diabetic patients and controls. In a study of patients following a 12-month program of intense physical activity, Raisanen *et al* (23) observed a greater improvement in DEC compared to weight, waist circumference or maximum oxygen volume (VO₂ max).

Therefore, taking into account the large number of methods used and the learning curve required to correctly implement these techniques as well as the absence of consensus as to which method is the most adequate to diagnose DSPN, the aim of this study is to validate the usefulness of DEC measurement in the early diagnosis of DSPN compared with traditional techniques in the Primary Care setting.

HYPOTHESIS AND OBJECTIVES

The hypothesis of our study is that the measurement of DEC is feasible, sensitive and specific and more or equally effective to other techniques commonly used in the initial screening of diabetic neuropathy in Primary Care.

Main objective

To evaluate the feasibility, effectiveness and performance of a new technique which measures DEC (sudomotor reflex) in the screening of diabetic neuropathy in Primary Care.

Specific objectives

1. Determine the performance of DEC (quantitative assessment of sudomotor reflex) as a tool for the screening of diabetic neuropathy in Primary Care compared with the Semmes-Weinstein 5:07 MFT when an EMG is used to confirm the presence of diabetic peripheral neuropathy in patients with prediabetes and type 2 diabetes.

2. Determine the performance of DEC (quantitative assessment of sudomotor reflex) as a tool for screening diabetic neuropathy in Primary Care compared with the Semmes-Weinstein 5:07 MFT when the UENS (Utah Early Neuropathy Score) is used to confirm the presence of diabetic peripheral neuropathy in patients with prediabetes and type 2 diabetes.

3. Estimate the cost and cost-effectiveness of the use of DEC in the screening of early diabetic neuropathy in Primary Care.

METHODS

Design

We will perform a blind, prospective study comparing DEC (sudomotor reflex) (Sudoscan®, Impeto Medical, France), EMG, the Semmes-Weinstein 5:07 MFT (10 g), the sensitivity of a vibrating tuning fork 128 Hz, the NDS score and the UENS score in a consecutive series of patients treated in Primary Care.

Sites

The Primary Care teams of Terrassa-Sud and other partners belonging to the Mutua Terrassa reference hospital and those of the University Hospital Sant Joan de Reus reference hospital.

Study subjects

We will consecutively include patients with type 2 DM over 40 years of age, with or without symptoms of neuropathy, attended in Primary Care. We will also include the following two groups of patients matched by age and gender: one including patients with prediabetes (intermediate alterations of glucose metabolism defined as impaired fasting glucose (IFG) and/or impaired glucose tolerance (IGT) determined by OGTT after 2-hour 75 g oral glucose administration and another including patients without glucose alterations (normal glucose tolerance) (control group).

Three main diagnostic categories (normal, pre-diabetes and diabetes) were defined using the WHO criteria based on 2-h postload glucose [<7.8 (140 mg/dL), 7.8–11.0 mmol/L (140-200 mg/dL) and / or fasting plasma glucose (6.1–6.9 mmol/L; 110-126 mg/dL) and >11.1 mmol/L (>200 mg/dL), respectively.

The exclusion criteria are: Type 1 DM, upper or lower limb amputation (except phalanges), diagnosis of neuropathy not related to diabetes, neuropathy by entrapment, use of psychoactive substances, chronic alcoholism, malnutrition; treatment with betablockers, presence of terminal disease or life expectancy less than 3 years. Pregnancy will be ruled out in women (negative pregnancy test) and a possible history of gestational diabetes will also be taken into account.

The study period is from January 1, 2017 to 30 November 2019.

Sample size

To estimate the validity and performance of a screening test that showed a sensitivity of 82%, a precision of 9% and a confidence interval of 95% (CI95%), considering a loss percentage of 20%, this study will include a total of 160 participants. The proportion of diabetes / prediabetes / normal glucose tolerance will be 2:1:1. The contribution by centres will be: 66% from the Mutua de Terrassa (106 cases) and 34% from Reus (54 cases).

Variables and dynamic data collection:

After verifying the inclusion criteria and receiving written informed consent to participate, during the **first visit** to the Primary Care centres the medical history of the patient will be obtained and a physical examination will be performed using the MFT and the NDS and UENS questionnaires will be given to screen for PN. The patient will also undergo DEC quantification using the Sudoscan® device.

The following variables were collected:

- Age, sex and country of origin.

- Family history of type1 or type2 DM: (yes / no).

- In diabetic population, length of diabetes evolution (in years) since diagnosis.

- Toxic habits: smoking (active smoker / ex smoker / non-smoker); drinking (teetotal, occasional drinker, habitual drinker).

- Other complications of diabetes and year of diagnosis (retinopathy, ischemic heart disease, peripheral vascular disease, cerebral vascular disease and diabetic nephropathy) will be collected from the patient medical records.

- Diabetes treatment.

- Other pharmacological treatments related to: hypotension, hypolipidemia, arterial thrombosis, among others.

On physical examination the following variables will be collected:

- Anthropometric data: Height (cm), weight (kg) (using validated clinical scale with stadiometer in light clothing), waist circumference (cm) (using a flexible measuring tape), measuring the point between the navel and upper iliac crest.

- Systolic/diastolic blood pressure; presence of pulses in pedia/posterior tibial arteries. Blood pressure (mmHg) measurements will be made three times while seated after 30 minutes of rest using a validated automatic device, with each measure being made at least one minute apart. The data recorded will be the mean of the second and third readings.

Other data to be collected include:

- Blood/urine tests: OGTT (Except in known DM); glycosylated hemoglobin A1c (High Resolution Liquid Chromatography (HPLC)), glomerular filtration rate [Modification of Diet in Renal Disease (MDRD) / Chronic Kidney Disease Epidemiology Collaboration (CKD-EPI)]; lipid profile (total cholesterol, triglycerides and LDL and HDL fractions using the cholesterol oxidase-phenol + aminophenazone (CHOD-PAP) method. These latter parameters should have been determined no more than 6 months previously. If not the determinations should be made in the reference laboratory.

- A score of 8 out of 8 with the Semmes-Weinstein 5:07 MFT(10 g) will be considered as sensitive.

A NDS score greater than or equal to 6 points will be considered as the presence of PN.
A UENS score greater than or equal to 10 points will be considered as the presence of PN.

- The determination of vibration sensitivity will be performed using a 128 Hz Rydel-Seiffer tuning fork. The test will be considered positive for PN when vibration of the tuning fork is not perceived when applied to the thumb or external maleolus.

In the **second visit**, done at the reference hospital, a neurologist blinded to previous test results, will perform neurographyc test including sensory conduction study of the median, ulnar and sural nerves, and motor conduction study of the deep peroneal nerve.

The studied variables will be amplitude of compound muscle action potential and distal latency of the motor nerves, and amplitude and distal latency of sensory nerves. DEC determination and the other neuropathy screening and electrophysiological tests will take no longer than one month.

The **third visit** will be carried out in the Primary Care centre where the results of the previous visit will be recorded and the patient will be informed of the results and the diagnosis.

The cost effectiveness of the different diagnostic methods studied will be evaluated and the incremental cost method to detect new cases compared to traditional methods will be calculated. In addition, a computer simulated model will determine the long term as well as the direct and indirect costs of the different methods.

STATISTICAL ANALYSIS

The Chi-square test will be used to analyse qualitative variables and the Student t-test will be performed for quantitative variables. Logistic regression will be used to identify predictors of diabetic neuropathy. Dependent variables (Response) will include the presence of diabetic neuropathy diagnosed by EMG or the NDS / UENS questionnaires. We will compare the performance of DEC with that of the MFT as screening tests of PN.

To determine the validity and reliability of DEC we will calculate the sensitivity, specificity, the positive and negative predictive values, and the positive and negative likelihood ratios. A ROC curve will be used and the area under the curve will be calculated. A p value <.05 will be considered as statistically significant. The analysis will be performed with the statistical packages STATA/SE 12.0 and R for Windows.

LIMITATIONS OF THE STUDY

The main limitation of the present study is accurate diagnosis of diabetic neuropathy since some studies have shown that some cases of diabetic neuropathy present no alterations in the EMG. Indeed, several considerations should be taken into account. Firstly, the EMG test is more specific, albeit not very sensitive, showing positive results in advanced stages of PN. The fingerboard and the NDS questionnaire are commonly used for the diagnosis of diabetic neuropathy, probably because the NDS is carried out prior to EMG and is actually often used to avoid the need for EMG. Therefore, both the EMG and the NDS score, which mainly assess the dysfunction of myelinated fibers provide a good profile for diagnostic confirmation. On the other hand, both the DEC and the MFT are able to diagnose and stage diabetic neuropathy earlier than the previous two tests by the detection of unmyelinated fiber dysfunction. But, another limitation is that MFT is a good test for prediction of a foot ulcer but is certainly insensitive for the detection of early neuropathy. For this reason, we think about the UENS, because of its sensitivity to early sensory loss and ability to record modest anatomic change in sensory function, considering patients with milder neuropathy. Therefore for purposes of simplification and taking into account the possible limitations, we will compare the effectiveness of the measurement of DEC and the use of MFT as diagnostic tools in Primary Care according to whether the true diagnosis is achieved by a) the EMG or b) the score of the NDS or UENS questionnaires.

Obviously there are another tests to detect early neuropathy, i.e. the Norfolk QOL-DN scale; but this questionnaire is not practical in the clinical scenario. Certainly, this test is a good tool to detect unaware neuropathy in patients with diabetes (24). This study used the Norfolk QOL-DN scale on 25000 patients with diabetes and found 6600 patients who were not aware of their neuropathy nor did their physicians know.

17

Another limitation of this study is the possibility of introducing a selection bias, and thus, we will consecutively include patients with type 2 DM, excluding patients with type 1 DM. We will also include a group of patients without DM or other glucose homeostasis disorders matched by age and gender to a 2:1:1 ratio (80 with DM, 40 with prediabetes and 40 with normal glucose tolerance).

QUALITY ASPECTS

This project will promote a strategy to determine whether the implementation of a new technique simplifies the detection of a major complication of diabetes, such as neuropathy.

Primary Care is clearly the most appropriate setting for the screening of this complication. Indeed, the earlier the diagnosis the better the prognosis. This strategic action on health is directly linked to:

(A) New medical technologies to promote personalized medicine based on the profiles of the individuals and not the disease.

(B) Translational and clinical research, evidence-based scientific and technological knowledge.

(C) Validation of a promising new technology for early detection of diabetic neuropathy in Primary Care.

(D) Application of evidence in clinical practice. This is a validation study of diagnostic technology implemented in real life conditions which would provide additional knowledge for everyday clinical practice.

It is of note that this study will also determine the cost-effectiveness of this new tool which is essential for the validation of new technologies aimed at different healthcare areas such as Primary Care.

Additionally, this project will establish synergies at different levels such as Primary

Care and Neurology, and the results can be shared with a number of centers, primary care areas and different scientific societies involved in the comprehensive care of patients with diabetes.

The results of previous studies support the feasibility of DEC in Primary Care, although further studies should be aimed at complementing and extending our hypothesis to different types of candidates and determining the cost-effectiveness of the systematic use of DEC.

Technical and collaborative aspects

The number of centres involved is limited, including Primary Care centres of the Catalan Institute of Health (ICS) of Reus (Tarragona) and the Mútua Terrassa (Barcelona).

In addition, IDIAP Jordi Gol and the Pere Virgili Health Research Institute - Hospital de Sant Joan (Reus), and IDIAP Jordi Gol and Mútua Terrassa have signed a cooperation agreement regarding research in the field of primary care.

Author's contributions

All authors substantially contributed to designing the study protocol or to data analysis and interpretation, and to drafting or revising the article. Specifically, JJC, TM and BC formulated the research question, designed the study (by cooperating with FB, RS, JV and GFO), and wrote the research proposal as well as the first draft of the manuscript. JJC, TM and BC discussed the proposal and his approach to the reality of primary care. BC, TM, FB, CLM, MGB, IB, NO and GFO critically revising the proposal for scientifical content.

All authors contributed to the revision of the manuscript, read and approved the final version.

Competing interests

The authors declare that they have no competing interests.

Ethics approval and consent to participate

The research ethics committee board at the Jordi Gol Research Institute (Barcelona) (www.idiapjordigol.org) approved the protocol (January 2015, reference number P14/147) and each participant signed a written informed consent.

FINANCIAL SUPPORT

The DECODING project was funded by: (1) First prize of the Research Grants of the CAMFiC (Catalonian Society of Family and Community Medicine), grant agreement no. XV/2014), (2) Grant from the Laboratorios del [name], S.A.U. and (3) Department of Health, Generalitat de Catalunya and the PERIS (*Pla Estratègic de Recerca i Innovació en Salut*) 2016-2020, grant agreement SLT002/16/00093. As DECODING is part of diabetes prevention projects (Catalan Diabetes Prevention Research Group), its team also participated in the grant agreements SLT002/16/00045, SLT002/16/00154 within this national call for research.

Members of the Catalan Diabetes Prevention Research Group

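### The ±9-point precision claimed for sensitivity with 160 participants rests on an unstated neuropathy prevalence; at the prevalences the protocol cites, the expected half-width is about ±10 to ±16 points

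*Combined protocol and SAP*

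**What the plan says.** The Sample size section is the only justification of the study's size. It gives "a sensitivity of 82%, a precision of 9% and a confidence interval of 95% (CI95%), considering a loss percentage of 20" per cent and concludes that 160 participants will be included. It then says "The proportion of diabetes / prediabetes / normal glucose tolerance will be 2:1:1". Limitations of the study gives the counts: "80 with DM, 40 with prediabetes and 40 with normal glucose tolerance".

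Specific objective 1 assesses DEC against monofilament testing "when an EMG is used to confirm the presence of diabetic peripheral neuropathy in patients with prediabetes and type 2 diabetes". Objective 2 names the same two groups, with UENS as the reference.

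The Introduction reviews neuropathy prevalence and remarks that "The prevalence of DSPN varies greatly according to the population, definition and detection method". Its figures include one study reporting prevalence "between 66% and 59% for type1 DM and type 2 DM, respectively (8"), a WHO report that "described a prevalence of 40% (8), and 50% in patients with more than 25 years of DM evolution", and a Spanish study that "published a figure of 24.1% (11"). It also cites a range of 25 to 48%. None of these is carried into the Sample size section, which states no prevalence, no number of participants with neuropathy and no reference standard.

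**The concern.** The denominator of sensitivity is the number of reference-positive participants, not the number enrolled. A sensitivity, a half-width, a confidence level and a loss rate together fix the number of cases. Getting from cases to total enrolment needs a prevalence, and none is given. A reader therefore cannot see where 160 comes from or whether the design can deliver ±9 points.

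The practical issue is how much the sensitivity estimate will tell a primary care reader about DEC as a screening test. The 95% Wilson interval is 71–90% for 47 of 57 cases detected, 67–91% for 31 of 38, and 63–93% for 19 of 23. The last of these is compatible with much poorer screening performance than a plan promising ±9 suggests.

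**Working it through.** **Inputs.** Sensitivity 0.82, half-width 0.09, 95% confidence (z = 1.96), 20% loss and N = 160 come from Sample size. The 80/40/40 split comes from Limitations of the study. The target groups, prediabetes and type 2 diabetes, come from Specific objectives. Prevalences of 59% (the figure for type 2), 40% and 24.1% (Spain) come from the Introduction. The 66% figure is for type 1 diabetes, which is an exclusion criterion.

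**Step 1: trying to reproduce 160.** Cases needed = z² × Se × (1 − Se) / d² = 1.96² × 0.82 × 0.18 / 0.09² = 70.0. Allowing for loss, 70 / 0.8 = 87.5, so 88 enrolled if every participant had neuropathy. The stated inputs alone do not give 160. Reading the 9% as a full width gives 280 cases, or 350 with loss, which does not give 160 either.

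**Step 2: the prevalence that would give 160.** Completers are 160 × 0.8 = 128, that is 64 with diabetes, 32 with prediabetes and 32 with normal glucose.

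- All 128 completers: 70 / 128 = 54.7%, and 70 / 0.8 / 0.547 = 160.
- The 96 with diabetes or prediabetes: 70 / 96 = 72.9%.
- The 64 with diabetes only: 70 / 64 = 109%, which is impossible.

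**Step 3: what the 55% route asks of the controls.** At 59% in diabetes plus prediabetes there are 0.59 × 96 = 56.6 cases. Reaching 70 then needs (70 − 56.6) / 32 = 42% of controls, about 13 of 32, to be reference-positive. At 40% there are 38.4 cases, and (70 − 38.4) / 32 = 99% of controls would have to be.

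**Step 4: half-width at the cited prevalences.** Half-width = 1.96 × √(0.1476 / n), with 0.1476 = 0.82 × 0.18 and n the expected number of cases after loss.

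| Prevalence | Diabetes + prediabetes (96) | Diabetes only (64) |
|---|---|---|
| 59% | 56.6 cases, ±10.0 | 37.8 cases, ±12.3 |
| 40% | 38.4 cases, ±12.2 | 25.6 cases, ±14.9 |
| 24.1% | 23.1 cases, ±15.7 | 15.4 cases, ±19.2 |

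Relative to the claim, the first column runs from 10.0 / 9 = 1.1 to 15.7 / 9 = 1.7 times as wide. On the same 96 completers, Wilson half-widths run from ±9.9 to ±15.2 and Clopper-Pearson from ±10.7 to ±17.0, so the choice of method does not change the picture.

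**Step 5: the no-loss case.** With no losses, 0.59 × 120 = 70.8 cases and the half-width is ±8.9. On the 120 with diabetes or prediabetes, ±9 is therefore met at 59% only if the loss the plan budgets for does not happen.

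**The case against.** The strongest reply is that this is not a miscalculation. An overall prevalence of 55% reproduces 160 exactly and lies inside the range the Introduction cites for diabetes. The main objective is not confined to diabetes and prediabetes, controls are enrolled, and Statistical analysis does not exclude them from the sensitivity estimate. Counting all 128 completers at 59% gives 75.5 cases and ±8.7, which meets the target.

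It is fair that 55% may have been the planning assumption and that the half-widths depend on the denominator. But the all-128 reading meets ±9 only at the highest type 2 figure, and only if that figure also holds in people with normal glucose. The other cited diabetes figures (24.1% to 50%) give ±9.4 to ±13.6 even on that basis.

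A second reply is that none of the cited prevalences is tied to this study's reference standards, and that applying a diabetes prevalence to prediabetes is an assumption. This stands. The prediabetes assumption favours the plan, since a lower value moves the result towards the diabetes-only column. The effect of the reference standard could go either way. The Introduction describes EMG as having poor sensitivity, so EMG-positive counts may be lower. UENS is chosen for its sensitivity to early loss, so its counts may be higher.

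Finally, at the most favourable type 2 figure the shortfall is one point, and the plan sets no pass/fail threshold for sensitivity. Both are true and limit the consequence.

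**Conclusion.** The concern holds. It is certain that ±9 points at 82% needs 70 evaluable reference-positive participants, and that the plan states neither this number nor the prevalence that would supply it. In the population named in objectives 1 and 2, 73% would have to be reference-positive, which is more than any prevalence the protocol cites.

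The size of the shortfall is conditional. With the cited diabetes prevalences applied to diabetes and prediabetes together, and the planned 20% loss, the expected half-width is about ±10 to ±16 points. If cases arise only in diabetes, it is about ±12 to ±19. These are illustrations, because no prevalence is given for prediabetes or for either reference standard as applied here. This should be fixed. It affects how the main accuracy estimate will be read, but it does not invalidate the study.

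**What to change.** Keep 160 and rewrite the justification so that it states the assumed prevalence in each glucose group, its source, the expected number of reference-positive completers, and the resulting half-width in place of ±9%. Suitable wording:

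> With 160 enrolled and 20% loss, we expect 96 completers with diabetes or prediabetes. If neuropathy prevalence in these groups is 24.1% to 59% (figures published for diabetes, assumed to apply to prediabetes), about 23 to 57 will be reference-positive, giving a 95% half-width of about ±16 to ±10 points at a sensitivity of 82%. If neuropathy occurs only in diabetes, we expect about 15 to 38 cases and ±19 to ±12 points.

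If about 55% overall was the planning assumption, say so, cite the source, and state the prevalence assumed in controls. In the analysis, report Wilson or exact intervals for sensitivity, with the case count for each reference standard.

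The cost is wording only, with no extra participants; the drawback is a less favourable stated precision. Holding ±9 instead, with the same ratio and loss and cases drawn from diabetes plus prediabetes, would need 70 / (prevalence × 0.75 × 0.8) enrolled: about 198 at 59%, 292 at 40% and 485 at 24.1%.
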